## 4.5 Study endpoints

### 4.5.1 Primary endpoint

The primary endpoint is the percentage of women with GDM treated with insulin therapy in the intervention group and the control group at delivery.

### 4.5.2 Secondary endpoints

Secondary endpoints include the following measures:

- Maternal endpoints
  - Changes in body weight (kg) from referral to delivery
  - Changes in HbA1c (mmol/mol) from referral to delivery
  - Time to insulin treatment onset (days) from study inclusion until prescription or delivery if insulin therapy is not initiated

- Mean prescribed initial and maximal insulin dose (units/kg body weight)
- Neonatal endpoints
  - Percentage of LGA new-borns
  - Percentage of new-borns small for gestational age (SGA)
  - Percentage of new-borns with macrosomia (birth weight >4,500 g)
  - Percentage of new-borns with neonatal hypoglycaemia (see definition in section 3)
  - Percentage of new-borns admitted to NICU

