### 3 Abbreviations and definitions of terms

BMI	Body Mass Index
Clinically relevant differences	Definitions of clinically relevant differences for all hypothesis-related outcomes will be reported in a statistical analyses plan (SAP). The SAP will be written and uploaded to clinicaltrials.gov before the statistical analyses will be conducted.
DDQOL	Diabetes Diet-related Quality of Life
DTSQ	Diabetes Treatment Satisfaction Questionnaire
EMR	Electronic Medical Record
GA	Gestational age
GDM	Gestational Diabetes Mellitus
HbA1c	Glycosylated haemoglobin A1c
HCCQ	Health Care Climate Questionnaire
Jaundice	Neonatal jaundice or neonatal hyperbilirubinemia is defined as elevated total serum bilirubin (TSB) (>68-137 $\mu\text{mol/l}$ ) and clinically manifests as yellowish discoloration of the skin, sclera, and mucous membrane.
LGA	Large for gestational age
Macrosomia	Macrosomia or foetal overgrowth is defined as birth weight >4,500 g
Neonatal hypoglycaemia	Neonatal hypoglycaemia is defined as plasma glucose level < 2.5 mmol/l after the first 2 postnatal hours.
NICU	Neonatal Intensive Care Unit
Non-white ethnic minority background	Non-white ethnic minority groups are defined as groups belonging to minority populations of non-European origin characterised by their non-white status. These include Asian (Indian, Pakistani, Bangladeshi, Chinese, any other Asian background), Caribbean, Black, African, Middle East, Hispanic/Latino, and any mixed or multiple ethnic background (1).
OGTT	Oral Glucose Tolerance Test.
PCDS	Perceived Competence in Diabetes Scale
PPAQ	Pregnancy Physical Activity Questionnaire
Preeclampsia	Preeclampsia is defined as new-onset gestational hypertension (with a blood pressure $\geq 140/90$ mmHg after 20 weeks of gestation in combination with proteinuria ( $\geq 0.3$ g protein in 24-hour urine specimen or $\geq 0.1$ g protein in a midstream urine spot), pulmonary oedema and/or specific symptoms of significant end-organ dysfunctions (e.g., headache, nausea, vomiting).
Preterm birth	Preterm birth is defined as GA less than 37 completed weeks
SD	Standard deviation
SGA	Small for gestational age
SOP	Standard operational procedure
Telemedicine	Telemedicine consultations are defined as tele- or video consultation
V	Visit

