## 4.3 Specific objectives

The overall objective is to investigate differences in clinical, cost-related, and patient-reported outcomes between women with GDM randomised to either intensive dietary therapy or standard dietary care.

The specific objectives are:

1. To investigate the effect of intensive dietary therapy on the likelihood of remaining treated with diet only vs. needing insulin therapy based on a hypothesis hierarchy (main objective)
2. To investigate the effects on maternal outcomes: changes in gestational weight gain; glycaemic control (HbA1c); gestational age at insulin initiation and prescribed insulin dose
3. To investigate the effects on neonatal outcomes: changes in birth weight; birth weight standard deviation score; neonatal hypoglycaemia; and admission to NICU
4. To describe changes in other pregnancy outcomes: number of cases of preeclampsia; preterm birth; mode of birth (caesarean section); jaundice; and macrosomia
5. To describe changes in patient-reported outcomes: treatment satisfaction; well-being; diet-related quality of life; autonomy support; and health competencies
6. To describe changes in dietary intake and physical activity
7. To describe if the intervention was conducted as planned, including number and type of visits
8. To describe hospital service costs related to the intensive dietary intervention compared with standard care in a cost-analysis.

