## 4.4 Hypotheses

1. Hypothesis hierarchy for the primary outcome (objective 1):  
The type I error will be controlled in the strong sense using the following hierarchical (fixed sequence A-C) testing procedure. This is based on priority ordering of the hypotheses and testing them in this order until an insignificant result appears:
  - A. We hypothesise that intensive dietary therapy is superior to standard dietary care (control group) in reducing the need for initiating insulin therapy in all women with GDM. Superiority will be claimed if the difference between the two groups is equal to, or surpass, the minimal important difference (defined as 50% reduction in need for initiating insulin therapy in the intervention group compared with the control group) in favour of the intensive treated group, and if the P-value is  $< 0.05$ .
  - B. We hypothesise that intensive dietary therapy is superior to standard dietary care (control group) in reducing the need for insulin therapy in women with a white ethnic background with GDM. Superiority will be claimed if the difference between the two groups is equal

- to, or surpass, the minimal important difference (defined as 50% reduction in need for initiating insulin therapy in the intervention group compared with the control group) in favour of the intensive treated group, and if the P-value is  $< 0.05$ .
- C. We hypothesise that intensive dietary therapy is superior to standard dietary care (control group) in reducing the need for initiating insulin therapy in women with GDM with a non-white ethnic minority background. Superiority will be claimed if the difference between the two groups is equal to, or surpass, the minimal important difference (defined as 50% reduction in need for insulin therapy in the intervention group compared with the control group) in favour of the intensive treated group, and if the P-value is  $< 0.05$ .
2. Hypotheses for secondary outcomes (objective 2 and 3):
- We hypothesise that an intensive dietary intervention in comparison with standard dietary care will induce:
    - a clinically relevant limitation in gestational weight gain
    - a clinically relevant improvement in HbA1c
    - a clinically relevant delay in insulin therapy initiation
    - a clinically relevant limited maximal insulin dose (units per kg body weight)
    - a clinically relevant reduction in birth weight at delivery at term
    - a clinically relevant reduction in birth weight SD at delivery

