#### Study visits

V0: Screening

V1: Baseline visit including one dietary consultation max 2 days after screening (both groups)

[figure not shown]
V2: Follow-up 1 with the dietitian max 2-3 days after V1 (only in the intensive group)

V3: Follow-up 2 with the dietitian a week after V2 (only in the intensive group)

V4: Follow-up 3 with the dietitian only if needed (only in the intensive group)

V5: Follow-up 4 with the dietitian only if needed (only in the intensive group)

V6: Telephone visit 2 weeks before delivery (both groups)

**Figure 1** Study design. Depending on GA at GDM diagnosis and time of delivery the intervention duration will be 5 – 20 weeks. Min. two follow-up consultations are provided in the intensive group.

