## 7 Examinations

All patients found eligible for inclusion in the study will be invited to a first study visit (V1) for collection of baseline measurements according to study specific SOPs. Subsequently, all participants will be randomised to one of the two study groups. All examinations will be performed in the outpatient diabetes clinic at SDCC. Study visits and examinations are described in detail in table 2 below, in the current section and section 5.4.

**Table 2:** Schematic overview of study visits

Visit	V0	V1	V6
Patient-related information			
Informed consent	X		
Assessment of in- and exclusion criteria	X		
Medical history	X		
Dietary history		X	X
Medication use		X	X
Randomisation	X		
Clinical efficacy outcomes			
Insulin use			X
Insulin dose (IE per kg body weight)			X
Time to insulin (days) from study allocation until prescription			X
Diet history interview		X	X
HbA1c		X	X
Body weight and height (height only at V1)		X	X
7-point SMBG		X	X
Questionnaires			
Socio-economic and ethnic characteristics		X	
Well-being (WHO-5)		X	X
Diabetes Diet-Related Quality of Life (DDRQOL)		X	X
Health Care Climate Questionnaire (HCCQ)		X	X
Perceived Competence in Diabetes Scale (PCDS)		X	X
Diabetes Treatment Satisfaction Questionnaire (DTSQ)		X	X
Pregnancy Physical Activity Questionnaire (PPAQ)		X	X

Abbreviations: SMBG, Self-Monitored Blood Glucose; V0, Screening, V1, data collected at baseline; V6, data collected pre-delivery.

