### *Prenatal care data*

Number and types of visits in each study group from referral to discharge after delivery:

- Type and number of visits with a dietitian (initial 60 min visit, 15-30 min follow-up visits, face-to-face, telephone or video)
- Number of visits with a midwife
- Number of visits with a nurse (individually)
- Number of visits with a nurse (in a group)
- Number of visits with an endocrinologist

Number of telephone contacts with an endocrinologist

Number of visits with an obstetrician  
Number of visits for ultrasonographic examination  
Number of visits including an interpreter (face-to-face, telephone or video)  
Body weight, kg at diagnosis and until delivery  
HbA1c, mmol/mol measured at diagnosis and until delivery  
Insulin-treated  
Time to insulin (days):  
- from study allocation until insulin prescription  
- from maternal GA  
Prescribed insulin, type, and dose (units/kg body weight)  
Prescribed antihypertensive medication, type, and dose  
Hospital admissions before delivery due to GDM  
Registered blood glucose measurements  
Preeclampsia

Labor data  
Induction of labour (yes vs no) and what weeks of gestation  
Preterm birth (defined as <37 weeks of gestation)  
Mode of delivery (vaginal delivery or caesarean section)

*Post-natal care*

Neonatal gestational age at birth  
Neonatal delivery weight, gram  
LGA  
SGA  
Macrosomia  
Jaundice  
Hospital days after delivery  
Neonatal hypoglycaemia  
Admission and number of days in NICU  
Stillbirth/neonatal death

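### The outcome behind the hypothesised delay in insulin start is defined for all women in 4.5.2, but only for women who start insulin in objective 2, Table 2 and section 7.3

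*Protocol*

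**What the plan says.** The Protocol describes the timing of insulin start in several places.

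- **Section 4.4, secondary hypotheses:** the intervention is expected to produce "a clinically relevant delay in insulin therapy initiation". The variable to be tested is not named.
- **Section 4.5.2, secondary endpoints:** "Time to insulin treatment onset (days) from study inclusion until prescription or delivery if insulin therapy is not initiated". Every woman has a value.
- **Section 4.3, objective 2:** "gestational age at insulin initiation and prescribed insulin dose". The first of these exists only for women who start insulin, and it is on a different time scale.
- **Section 7, Table 2, under clinical efficacy outcomes:** "Time to insulin (days) from study allocation until prescription". Nothing is said about women who never start.
- **Section 7.3, prenatal care data:** time to insulin is listed "from study allocation until insulin prescription" and also "from maternal GA".

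The starting point differs too: inclusion in 4.5.2, allocation in Table 2 and 7.3. Section 3 leaves the size of a clinically relevant difference to the statistical analysis plan, which is not available here. Follow-up varies widely between women, since "the intervention duration will be 5 – 20 weeks" (Figure 1).

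**The concern.** These are different variables with different populations. The 4.5.2 version keeps both randomised groups whole. The versions that need a start date compare only women who started insulin, and whether a woman starts is itself the primary endpoint. If the intervention works as planned, the starters in the intensive arm are a smaller and differently selected group than those in the control arm. Their difference in onset time is then not a randomised comparison.

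The practical risk is that the reported result depends on which definition is taken up at analysis. A starters-only comparison can hide a benefit or show apparent harm. A mean of days over all women can present prevention as postponement. A threshold for a clinically relevant delay cannot be set sensibly until the variable is fixed.

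**Working it through.** **Inputs from the Protocol.** Section 8 gives a control incidence of 50% in the selected population and a 50% relative reduction, hence 25% in the intensive arm. Planned N is 214, or 107 per arm. Follow-up is 5 to 20 weeks (35 to 140 days).

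**Check on the incidences.** The Protocol states no figure for time to insulin, so there is none to reproduce. Table 3 does show which incidences underlie the design. With an unpooled normal approximation and two-sided alpha 0.05, 50% vs 25% gives power 0.789 at N = 107 (stated 0.80), and 0.974 at N = 214 (stated 0.98). For subgroups of half that size, power at N = 214 is 0.789 (stated 0.80). The 30% vs 15% pair gives 0.761 for all women at N = 214 and does not fit. I therefore use 50% vs 25%.

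**Expected starters.** 107 × 0.50 = 53.5 in control and 107 × 0.25 = 26.75 in the intensive arm, so about 54 vs 27.

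**Step 1: a mean over all women with delivery as the end value.** Let F be time to delivery and m mean onset among starters, the same in both arms, so nobody is delayed. Then

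difference = (0.25m + 0.75F) − (0.50m + 0.50F) = 0.25(F − m).

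Assuming m is one third or one half of F:

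| F (days) | m = F/3 | m = F/2 |
|---|---|---|
| 35 | +5.8 | +4.4 |
| 84 | +14.0 | +10.5 |
| 140 | +23.3 | +17.5 |

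The starters-only difference is 0 throughout. With 30% vs 15% the factor would be 0.15, and each figure would fall to 60% of that shown.

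**Step 2: which starts are prevented.** Assumptions: inclusion at 24–32 weeks, delivery at about 39.5 weeks, mean F = 80.5 days, and control onset uniform over the first 70% of F. The control starters' mean is then 0.35F, and the control all-women mean is 0.5 × 0.35F + 0.5F = 0.675F.

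- Prevented at random: intensive all-women mean 0.25 × 0.35F + 0.75F = 0.8375F; difference 0.1625F = 13.1 days.
- Later half prevented: intensive starters' mean 0.175F. Starters-only difference −0.175F = −14.1 days. All-women difference (0.25 × 0.175 + 0.75 − 0.675)F = 0.11875F = 9.6 days.
- Earlier half prevented: intensive starters' mean 0.525F. Starters-only difference +0.175F = +14.1 days. All-women difference 0.20625F = 16.6 days.

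A simulation of 400,000 women per scenario agrees. The table shows intensive minus control; the rate ratio is starts per day of insulin-free follow-up, with non-starters followed to delivery.

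| Scenario | All women, mean of days | Starters only | Rate ratio |
|---|---|---|---|
| Half of starts prevented at random | +13.3 | +0.2 | 0.40 |
| Later starts prevented | +9.5 | −14.1 | 0.43 |
| Earlier starts prevented | +16.5 | +14.2 | 0.38 |
| All starts 14 days later, none prevented | +6.9 | +13.9 | 0.89 |
| No insulin effect, intensive arm delivers 7 days earlier | −3.6 | about 0 | 1.07 |

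Gestational age at initiation follows the starters-only column to within about 0.2 days. A separate simulation with other assumptions (107 per arm, mean onset 4 weeks, delivery about 12 weeks after inclusion) gave +14.7 and +0.1 days for random prevention, and +11.5 and −12.4 days when later starts were prevented.

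**Step 3: time origin.** V1 is at most 2 days after screening, and the gap precedes randomisation. It adds at most about 2 days to each woman's time and no expected difference between arms.

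**The case against.** A reader might infer that 4.5.2 records the delivery date as the date of insulin onset. The document does not support that. The sentence is ordinary time-to-event wording, in which observation ends at prescription or, failing that, at delivery. No mean is specified for this item, although the next item in the same list does name one. Read as follow-up ending at delivery, the three prevention scenarios give consistent rate ratios of 0.38 to 0.43, with no change of sign. How delivery is handled may properly be settled in the statistical analysis plan.

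It can also be said that Table 2 is a schematic and 7.3 a list of items to extract, so both may be shorthand rather than rival definitions. Incomplete for non-starters is a fair description of them. The hypothesis is one of eight secondary ones outside the A–C hierarchy, so no controlled error rate is at stake.

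All of this stands, but it does not remove the conflict. Objective 2 names a different variable, defined only in starters, and Table 2 lists its version as an efficacy outcome. Section 4.4 does not choose between them, and section 3 defers only the relevant differences, not the outcome's definition. Nor does the time-to-event reading isolate a delay: random prevention with no postponement gives 0.40, while a true 14-day postponement gives only 0.89.

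**Conclusion.** The inconsistency is real and can affect the conclusion. Section 4.5.2 covers all women; objective 2, Table 2 and 7.3, as written, give a value only for starters, who are expected to be 50% of one arm and 25% of the other. A starters-only comparison can then show nothing, or earlier onset by about 12 to 14 days in the two simulations, while the all-women version favours the intervention.

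The incidences come from section 8. The day figures rest on assumed onset distributions and on assumptions about which starts are prevented, so they show that the answer depends on the definition and do not predict a result. The figure of roughly 4 to 23 days applies only if a mean is taken with delivery as the end value, which the Protocol does not say. Nor should the differing time origins be read as a bias; aligning them is a consistency correction only. Severity is minor to moderate, for a secondary outcome.

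**What to change.** Use one definition in 4.3, 4.5.2, Table 2 and 7.3: time from randomisation to first insulin prescription, in all randomised women. State that delivery ends follow-up as a competing event, and compare cumulative incidence of insulin start by arm instead of a mean of days. Have 4.4 refer to that variable.

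Keep gestational age at initiation among starters as a descriptive item, labelled as such. Do not claim a delay separate from prevention, since this comparison reflects both. Use randomisation as the single time origin.

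The cost is wording in the Protocol and matching text in the statistical analysis plan, to be settled before analysis. Prescription, randomisation and delivery dates are already collected, so no new data are needed.

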Insulin therapy can improve glycaemic control and has been shown to be effective in reducing the rate of macrosomia in GDM (20). But use of insulin during pregnancy is also associated with several clinical implications (e.g., increased risk of maternal hypoglycaemia) (6, 14, 21), increased hospital costs (endocrinologist visits, extra visits to other health care professionals, additional ultrasonographic examinations depending on the time of insulin initiation), and medical costs (insulin) (22) as well as higher costs in relation to delivery (e.g., induction of labor, pre-term delivery) (14), and neonatal care (increased risk of neonatal hypoglycaemia) (23, 24). Finally, the personal burden associated with insulin

use (e.g., extra worries, additional SMBG measurements, and insulin injections every day) also affects women with GDM (25). Only one smaller case-control study has looked at quality of life (QoL) in GDM and found no differences between the diet-treated vs. insulin-treated group (26).

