    - a clinically relevant reduction in neonatal hypoglycaemia
    - a clinically relevant reduction in new-borns admitted to NICU
3. Objectives 4-7 are regarded descriptive
4. Hypothesis for hospital care costs related to the intensive dietary intervention (objective 8):
- We hypothesise that an intensive dietary intervention in comparison with standard dietary care will have a positive effect on the net hospital costs, or at least be cost neutral (non-inferiority) if insulin therapy can be prevented for some of the women. The reason being that insulin therapy is associated with more cost intensive GDM treatment during pregnancy, higher expenses for inducement of labour, and higher cost of adverse events for mother and child as caesarean section and NICU stay, and length of hospital stay. The cost will be estimated from referral with GDM to discharge of mother and offspring.

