## 5 Investigational study design

### 5.1 Study design

The INTENSE-GDM trial is a randomised controlled parallel group open-label effectiveness trial aiming to include 214 women with GDM (Figure 1). Participants will attend one consultation with a dietitian in the standard care group and up to 5 consultations with a dietitian in the intensive dietary counselling group. Both groups will receive one end-of-intervention telephone call. Each study visit is described in detail in section 5.4.

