**Table 1. Data collection procedures in the INTENSE-GDM Trial**

Variable	Measurement	Participant	Screening V0	Baseline V1	Pre-delivery V6	Post-delivery No visit
Ethnicity and socio-economic status	Self-constructed questions	W		•		
Medical history	EMR	W	•	•		
Dietary history	Personal interview	W		•	•	
Alcohol, sleep, and smoking	Self-constructed questions	W		•	•	
Obstetric history	EMR	W		•	•	•
Medication	EMR	W		•	•	
Glucose control	HbA1c	W		•	•	
	7-point SMGB	W		•	•	
	Neonatal hypoglycaemia	N				•
	Admission to NICU	W, N				•
Anthropometry	Height, BW, BMI	W		•	•	
	Delivery weight (EMR)	N				•
	LGA (EMR)	N				•
	SGA (EMR)	N				•
	Macrosomia (EMR)	N				•
Delivery complications	Preterm birth (EMR)	W				•
	Preeclampsia (EMR)	W				•
	Caesarean section (EMR)	W				•
	Jaundice (EMR)	N				•
Well-being	The WHO-Five Wellbeing Index (WHO-5)(33)	W		•	•	
Diet-Related Quality of Life	Diabetes Diet-Related Quality of Life (DDRQOL) (34)	W		•	•	
Autonomy support	Health Care Climate Questionnaire (HCCQ) (35)	W		•	•	
Perceived competences	Perceived Competence in Diabetes Scale (PCDS) (35)	W		•	•	
Treatment satisfaction	Diabetes Treatment Satisfaction Questionnaire (DTSQ) (36, 37)	W		•	•	
Physical activity	Pregnancy Physical Activity Questionnaire (PPAQ) (38)	W		•	•	
Adherence	EMR data	W				•
Hospital costs	EMR and registry data	W, N				•
Safety	Adverse events	W			•	•

BMI, Body Mass Index; BW, Body weight; EMR, Electronic Medical Record; HbA1c, Haemoglobin A1c; W, Woman with GDM; N, neonate delivered by women with GDM in the study; NICU, neonatal intensive care unit.

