## 7.3 Electronic medical record data

The written consent provides the trial investigators, the sponsor, the sponsor's representatives, and regulatory authorities direct access to obtain information from the patient's medical records, including electronic records, with the purpose of reviewing information regarding the participant's health condition. This access is necessary for conducting the research project and for regulatory oversight, including self-regulation, quality control, and monitoring, which they are obligated to perform. According to planned and described procedures, the research dietitians will access the participant's medical record to collect information relevant to the study as described under screening (assessment of in- and exclusion criteria), collection of medical history, concomitant medications, and clinical outcomes from referral until discharge after delivery. The purpose of obtaining information from the medical records is to assess whether the women is eligible for inclusion, to describe the study population, and report study outcomes related to pregnancy and child delivery.

The following data from the mother's and infant medical records and The National Patient Register will be collected (see Table 1 for details about data sources):

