## 8 Sample size determination

A 50% difference in the incidence of insulin therapy between the two study groups during the study period was defined as the minimally important difference for the primary outcome. The sample size estimation was based on a logistic regression model (outcome = group) and the following assumptions: An allocation ratio of 1:1; alpha = 0.05; 0.8 power, an incidence of insulin therapy of 30% in the usual care group and 15% in the intervention group in need of insulin therapy. The expected incidence in the standard care group is based on register data from Herlev Hospital in the period 2019-2022 showing that approximately 30% of the women with GDM referred to the hospital had been prescribed insulin. Since we are only investigating women with GDM with an estimated risk of insulin therapy above 20% based on our inclusion criteria), our analysis shows that it will result in an incidence of 50%. Thus, we aim to include 214 women (see table 3 for sample size estimations), but if fewer women are included, we will only test the main hypothesis for all participants whereas subgroup-analysis testing based on ethnicity (white\_nonwhite) will be exploratory.

**Table 3:** Sample size estimations

N Total	Power All	Power Subgroups
107	0.80	0.51
150	0.92	0.65
175	0.95	0.72
200	0.97	0.78
214	0.98	0.80

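### Neonatal hypoglycaemia is taken from routine records without noting which new-borns were tested, so a testing difference that follows maternal insulin could not be told from a real reduction

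*Protocol*

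**What the plan says.** Section 4.5.2 names the endpoint as "Percentage of new-borns with neonatal hypoglycaemia (see definition in section 3"). Section 3 gives the definition: "Neonatal hypoglycaemia is defined as plasma glucose level < 2.5 mmol/l after the first 2 postnatal hours". Section 4.4 hypothesises "a clinically relevant reduction in neonatal hypoglycaemia", so the endpoint is one of the hypothesis-related secondary outcomes and not merely descriptive.

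On data collection, Table 1 places neonatal hypoglycaemia in the column headed "Post-delivery No visit". Section 7.3 states the source: "The following data from the mother's and infant medical records and The National Patient Register will be collected". Its post-natal list then has one entry for this outcome, the name of the condition, with no value, time or number of tests. The same section asks for underlying measurements elsewhere: the OGTT value in mmol/l, HbA1c, and the blood glucose measurements listed under prenatal care.

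The trial is described in section 5.1 as a "randomised controlled parallel group open-label effectiveness trial aiming to include 214 women with GDM". Its primary endpoint is insulin use, with a halving set as the minimal important difference (sections 4.4 and 8). In listing the cost implications of insulin, section 4.1.3 mentions "neonatal care (increased risk of neonatal hypoglycaemia").

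**The concern.** Under the section 3 definition, a new-born can become a case only if somebody measured plasma glucose after 2 hours. The protocol sets no sampling common to both arms, so whether a measurement exists depends on routine care. If routine care takes maternal insulin into account, the chance of being tested depends on the very variable that the intervention is meant to change. The arm with less insulin would then have fewer recorded cases at the same true glucose distribution.

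The risk is that a difference in detection is reported as a neonatal benefit. A rule in the SAP for untested new-borns would help only if the data show which new-borns these are, and section 7.3 does not list that information.

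**Working it through.** **No stated figure to reproduce.** The protocol gives no rate, effect size or power for neonatal hypoglycaemia. The only figures to anchor are the insulin rates.

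**Insulin rates (section 8).** The text first gives 30% vs 15%, then says that for the selected population "our analysis shows that it will result in an incidence of 50" per cent. A halving makes this 50% vs 25%. Table 3 shows which pair underlies the plan. With power = Φ(|p1 − p2| / √[(p1(1 − p1) + p2(1 − p2))/n] − 1.96) and n per arm:
- 50% vs 25%, N = 107: 0.25/√(0.4375/53.5) − 1.96 gives 0.789 (Table 3: 0.80).
- 50% vs 25%, N = 214: 0.25/√(0.4375/107) − 1.96 gives 0.974 (Table 3: 0.98).
- 30% vs 15%, N = 214: 0.15/√(0.3375/107) − 1.96 gives 0.761 (Table 3: 0.98).

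The illustration therefore uses 50% vs 25%, with 30% vs 15% alongside.

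**Model.** Recorded rate in an arm = h × [q × tI + (1 − q) × tD], where
- h = true risk, assumed equal in all new-borns, so there is no true effect;
- q = share of mothers on insulin (section 8);
- tI, tD = shares tested after insulin-treated and diet-only pregnancies (assumptions, not in the protocol);
- an untested new-born yields no recorded case (also an assumption).

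The risk h cancels in the ratio of intensive to standard care. With tI = 0.95:

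| tD | Ratio at 50% vs 25% | Spurious reduction | Ratio at 30% vs 15% | Spurious reduction |
|---|---|---|---|---|
| 0.95 | 1.000 | 0% | 1.000 | 0% |
| 0.80 | 0.8375/0.875 = 0.957 | 4% | 0.8225/0.845 = 0.973 | 3% |
| 0.60 | 0.6875/0.775 = 0.887 | 11% | 0.6525/0.705 = 0.926 | 7% |
| 0.50 | 0.6125/0.725 = 0.845 | 16% | 0.5675/0.635 = 0.894 | 11% |
| 0.20 | 0.3875/0.575 = 0.674 | 33% | 0.3125/0.425 = 0.735 | 26% |

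For example, the numerator for tD = 0.80 at 50% vs 25% is 0.25 × 0.95 + 0.75 × 0.80 = 0.8375.

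**In numbers of new-borns.** Assume h = 20% and 107 new-borns per arm. At tD = 0.50 the recorded rates are 0.20 × 0.725 = 14.5% and 0.20 × 0.6125 = 12.25%, or about 15.5 vs 13.1 cases.

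**Chance of a significant false benefit.** With 107 per arm, h = 20%, 50% vs 25% insulin and tI = 1, the two-proportion normal approximation (two-sided 0.05) gives 4%, 8%, 14% and 28% for tD = 0.75, 0.50, 0.25 and 0. Without bias it is 2.5%.

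**Can the listed data reveal it?** In new-borns of diet-only mothers, the recorded rate estimates h × tD. Without tested yes/no, low risk with full testing looks the same as higher risk with partial testing.

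**The case against.** **The SAP may deal with untested new-borns.** This stands. The protocol contains no rule that an untested new-born is a non-case. A reader might infer one from the denominator of all new-borns, but the endpoint is a one-line label worded like its neighbours, and a rule may be set in the SAP, which is not shown. Its absence is no fault here. What remains is the data list: an analysis rule cannot be applied to information that was not extracted.

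**Unequal testing is not documented.** This also stands. A reader might infer that fewer insulin-treated mothers would by themselves produce the hypothesised reduction. The protocol does not support this: it nowhere says that testing depends on insulin, every mother in the trial has GDM, and with equal testing the bias is exactly zero.

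**The protocol speaks of risk, not testing.** Correct. Section 4.1.3 reports a higher risk of neonatal hypoglycaemia with insulin, so a reduction through less insulin could be a real, mediated effect. The equal-risk assumption in the illustration isolates the detection effect and is not a claim about these mothers. The possibility of a real effect makes it more useful to be able to tell the two apart.

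**The abstractor will see the dated values anyway.** This is plausible, since applying the definition means looking at the infant's record, and section 7.3 lists variables without specifying a case report form. But what is seen is not necessarily kept, and only the condition is listed. Maternal insulin is recorded, yet splitting by it conditions on a post-randomisation outcome and still does not show who was tested.

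**The effect is small over much of the range and concerns one secondary endpoint.** This is true and is reflected in the verdict.

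**Conclusion.** The point holds in a conditional form. The endpoint needs a glucose value, the value comes from routine care, and the protocol does not plan to record whether it exists. If testing is more frequent after insulin-treated pregnancies, the comparison is biased towards the intervention, and the listed data could not show it.

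The size cannot be derived from the protocol. Under the stated assumptions at 50% vs 25% insulin it runs from nothing, through 4% to 16% for testing of 80% to 50% of diet-only new-borns, to 33% at 20%; at 30% vs 15% the figures are 3% to 11%, and 26%. No stated figure is shown to be wrong, and the primary endpoint is not affected. This is a cheap improvement, not a flaw that undermines the trial.

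**What to change.** - In section 7.3, add for each new-born: plasma glucose measured after the first 2 hours (yes/no), number of such measurements, and the first and the lowest value. The number matters because repeated testing gives more chances of a low value.
- Keep the section 3 definition of a case unchanged.
- Report the share tested by arm beside the endpoint.
- Add a sensitivity analysis in which untested new-borns are treated as unknown and not as non-cases. Limiting the analysis to tested new-borns is one form, but they may be a selected group, so it should be read together with the share tested.

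The cost is a few more fields from records that the trial already accesses, and one further analysis. Neonatal care does not change. The downside is that a favourable result may become less certain.
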